One way to increase the control of upper limb movement is through the use of a specialized robotic technique based on error augmentation (EA) (see Israely and Carmeli 2016 for recent review). In EA treatment, subjects are provided with feedback that enhances their motor errors and forces them to move into larger joint ranges. This is usually done by distorting visual feedback while additional haptic feedback can be provided using robotics. EA has resulted in positive effects for lower limb locomotor training, e.g., Kao et al. 2013; Tyrell et al. 2015). Recently, several researchers have implemented EA for upper limb training, but results have been disappointing in terms of functional improvement (e.g., Abdollahi et al. 2014; Molier et al. 2011). It is likely that the reason for the lack of functional effects is that the error enhancement is only applied in a generalized way, without consideration of the specific upper limb motor deficit of the patient; i.e., the training is not personalized to the patient's particular motor impairment.

In previous work, we have tested the effect of a patient-specific impairment-based training approach based on the threshold control theory (TCT) of motor control (Feldman 2015) in a tri-national randomized controlled trial (IDRC/CIHR/ISF 2015-20). According to TCT, voluntary movement is generated by regulating the spatial thresholds (STs) at which muscle activation begins. EMG emerges based on the interaction of the biomechanics of the system with the environment. The ability to regulate STs is reduced in patients with stroke, due to damage to descending neural pathways ([name] and Feldman 1994). The reduced capability leads to abnormal muscle activation patterns (i.e., excessive co-activation) as well as spasticity and weakness within well-defined spatial (angular) zones. The **active control zone**, i.e., the angular zone in which voluntary movements can be made with typical muscle activation patterns, is reduced. Thus, in the previous trial

([name] et al. 2018), the upper limb training was optimized to increase the patient's active control zone of the elbow joint by identifying and restricting reaching movements to that specific zone. Preliminary results suggest that this approach led to greater gains in upper limb function in the group who had individualized training compared to the group that did not.

Studies suggest that errors made during training improve later performance of the task. For example, in a study in which elderly subjects practiced rhythmic motion of the upper limb with and without visual feedback, greater errors made during treatment led to more movement improvement following training (Levy-Tzedek 2017). This result is consistent with the TCT as muscle activation is regulated by the difference between the actual limb position and referent limb position specified by the brain. The referent position also plays a role in the perception of the actual limb position, while the afferent component identifies the deflection of the limb from the referent limb position. Based on this combination, the system identifies the movement error, i.e., deviation of the limb from the target position. Movement correction is accomplished by properly adjusting the referent limb position.

The sensitivity of referent control may be enhanced by augmentation of the movement error, i.e., Joint Error Augmentation (JEA). Furthermore an improvement in referent limb control is likely to be associated with improvement in threshold (referent control) at the level of individual joints. Development of rehabilitation treatment protocols based on motor control theory, such as that underlying JEA, is a promising direction for robotic rehabilitation therapy.

Research Objectives:

Our goals are to investigate the effect of JEA on motor learning in healthy subjects and on upper limb rehabilitation in subjects with stroke.

Hypothesis 1: In both groups, JEA applied to the elbow joint range will lead to better learning of movement speed and precision of a reaching task compared to no JEA.

Hypothesis 2: In patients with stroke, JEA applied to the elbow joint range will lead to a greater increase in the patient's active control zone at the elbow compared to no JEA and thus in his/her ability to perform isolated voluntary movement of the elbow.

Research plan

In our preliminary proof of principle study, we developed and tested a passive robotic system in 21 healthy subjects (aged 26.2, SD 1.2 yrs). A passive robotic arm was developed for supporting and monitoring arm motion and combined with a simple virtual reality pick-and-place game (Srör et al. 2018). Software was developed for integrating input from the robotic arm and a Kinect camera. The software includes a pick-and-place VR game, game success feedback, and motion feedback with and without JEA. Individuals were assigned to a training group with or without EA and performed one 30 min training period. There was no difference between groups in terms of the success rate of hitting the targets. The group training with EA tended to work longer and be more motivated. The application was found to be acceptable to healthy individuals, to enhance motivation to exercise and not to cause fatigue or any adverse effects (Srör et al., 2018; 2019a; 2019b).

The next phases of the study are to investigate the effects on learning with JEA feedback in healthy subjects, and then to test the JEA feedback effect in patients with stroke.

In two separate studies, we will test 24 healthy subjects and 24 patients who have moderate-to-severe stroke (spasticity + some arm movement). Testing of the healthy subjects will be done in Canada and testing of patients will be done in two countries (Israel-Soroker Hospital, Beer-Sheva; Canada-Jewish Rehabilitation Hospital, Laval/Montreal). The motivation for testing the application in patients at two sites is to assess the feasibility of conducting a multi-site study using this technology.

In both studies: Subjects will be randomly allocated to two equal groups. One group (control) will receive regular feedback and the other group will receive JEA feedback (randomized with catch trials).

Subjects will perform ~30 min of target reaching with their non-dominant/affected arm, 3 times in one week, with a minimum of 1 day between sessions. Rest periods will be provided when needed to avoid subject fatigue. In the experimental group, target locations will be tailored to coincide with active control range limits determined at the beginning of each session. In the stroke group, workspace extensions will be added as active range increases (i.e., exercise progression) for patients receiving JEA feedback.

Session 1 (1 hour and 15 min) will include a Reaching Pre-Test of 10 trials to a fixed target (see below), reaching training and evaluation of perceived exertion. Session 2 (1 hour) will include the evaluation of the TSRT in the stroke group, reaching training and perceived exertion rating. Session 3 (2 hours) will be the same as Session 2 but the last 10 trials of Session 3 will be done to a fixed target (Post-Test). Following Session 3, there will be a pause of 1 hour after the training and then a Reaching Follow-up Test of 10 trials to a fixed target will be done. In addition, the stroke group will undergo a clinical evaluation including determination of the elbow flexor TSRT angle prior to Session 1 and another clinical evaluation following Session 3.

For Study 1, the primary outcome measures are change in the index of performance (IP), which is a measure of reaching efficiency (Takeda et al., 2019).

For Study 2, the primary outcome measures are the same as those for the healthy group as well as the area of the active control workspace based on the TSRT and spasticity. The **secondary outcome measures** are the change in the FMA-UL and patient effort according to the Borg scale.

Evaluations for Study 2:

Clinical evaluation sessions: Clinical assessments will be conducted by a blinded assessor before (Pre-test) and after (Post-test) the last training session. In the Pre and Post-test sessions, all of the following assessments will be done.

Arm motor impairment: **i) Voluntary arm motor ability and coordination** will be evaluated using the valid (Berglund and Fugl-Meyer 1986) and reliable Fugl-Meyer Arm Assessment (FMA; Fugl-Meyer et al. 1975) that measures reflexes, volitional movements and UL

coordination on a 66 point scale. FMA also evaluates sensation (light touch), kinaesthesia and passive range of motion on ordinal scales; **ii) spasticity** will be measured by the Modified Ashworth Scale (Bohannon and Smith 1987) on a scale of 0 to 4 ; **iii) TSRT** The *threshold of the active control zone* of the elbow will be identified by determining the tonic stretch reflex threshold (TSRT) angle in elbow flexors using the Montreal Spasticity Measure (Calota et al. 2008). This methodology has been successfully implemented in our previous RCT ([name] et al. 2018). It consists of recording electromyographic signals from the elbow flexors and extensors with surface electrodes as well as the elbow angle using a goniometer, while the elbow is stretched from flexion to extension 20 times. Then, determination of the active control workspace will be done by passively moving the arm attached to the robot arm at a moderate speed throughout the horizontal workspace while monitoring elbow extensor and flexor EMG on an oscilloscope and respecting the identified elbow joint range limitation. Since, no EMG activity should be present at rest, the appearance of elbow flexor or extensor activation during passive manipulation of the arm through the horizontal shoulder/elbow workspace will indicate that the elbow has been moved beyond the TSRT angle. In this way, the TSRT angle will define the limits of the whole arm active control workspace. The area of the active control workspace will be computed from the x, y workspace recorded by the Kinect II camera using enhanced tracking and expressed as a percentage of the full biomechanical workspace defined by the limits of the passive shoulder horizontal/elbow area.

Fig. 1. Training position and set-up.

For both studies: Training protocol (Fig 1): As described above, the arm active control workspace will be measured by the Kinect II camera and reproduced in the VR workspace for each session. Objects to be reached will be displayed within this defined VR workspace for both groups. In this way, the training will be personalized to the range of active motion in each subject. Three 30 min training sessions will be done. At the end of each training session, the patient's perceived *sense of effort* will be evaluated with the valid and reliable 20 pt Borg Rating of Perceived Exertion Scale (Borg 1982).

The robotic system consists of an ergonomic double-joint horizontal manipulandum mounted on a rigid, movable support (Fig. 1). The subject sits in an armless chair with a high back support and trunk movement is restricted. The forearm is attached to the manipulandum with Velcro and the wrist and hand are free to move. Movements of the arm and manipulandum are used as input signals to move the arm avatar in the VR game. For the stroke group, the game (Fig. 2) is adapted to patient capabilities, based on her/his active control range for isolated elbow flexion and extension determined before each training session. The initial hand position is 10 cm sagittal to the patient's midline. Prior to

Session 1, a Pre-Test will be conducted in which subjects will reach 10 times to a fixed target placed at arm's length in the subject midline. The same protocol will be added to the end of Session 3 as a Post-Test and repeated 1 hour after Session 3 as the Follow-up Test.

Training Protocol: Objects to be reached are randomly presented within the virtual workspace every 2-10s. The subject is instructed to reach each object from the specified starting position as quickly and as accurately as possible in a session of at least 30 minutes (approximately 138 reaches, considering 3s/reach). To control training intensity, practice will be extended to the time needed to complete 138 reaches per session. During reaching, the motion of the whole arm is shown by an avatar, while vision of the subject's actual arm is blocked by a screen, to minimize visual-proprioceptive mismatch (Dietz 1992). For JEA trials, the avatar depiction includes a 10° elbow flexion error based on forward kinematic calculation. For implicit learning to occur,

we will use a small (i.e., 10°) instead of a large error, to decrease direct perception of elbow position and conscious correction. Feedback in the form of task success of endpoint (hand) movement is presented at the end of each reaching trial to increase motivation and engagement (Guadagnoli and Lee 2004). The introduced error causes the subject to perceive their hand position as undershooting the target. The subject's task is to solve the problem of moving the arm further by learning to incorporate more elbow extension into the whole arm reaching task. Multiple solutions are needed in order to solve problems for targets located in different parts of the arm workspace. **Game difficulty** will be progressed according to the Challenge Point theory of motor learning (Guadagnoli and Lee 2004), which suggests that learning is enhanced by optimally challenging the individual through manipulation of task difficulty according to their motor skill level and cognitive capacity. Difficulty level will be increased by altering target locations (i.e., based on changes in active ranges for the JEA stroke group and by increments of 2 cm for the non-JEA group) and by decreasing the allowable movement time for each reach (increasing movement speed). Difficulty will be progressed when the participant reaches a 90% success rate. Low-cost motion tracking is used for clinical accessibility. **Motion tracking** is based on the Kinect II skeleton and an extended Kalman filter (Simon 2006) to improve accuracy (Fig. 3). A Kalman filter has two steps in each iteration. First, a prediction is made based on the current location and the motion model. The prediction is of both the state variables and their uncertainty. Then, the predictions are updated based on the current measurement using a weighted average, which incorporates the uncertainties of the measurements and the predicted states. The model assumes no shoulder motion, and motion along the same direction as in the previous step in the elbow and wrist. At each step, model predictions are combined with the measured locations, where weights are based on the Kalman gain calculated on the estimated state error. Due to the incorporation of rigid body relations,

[figure not shown]

Fig. 2. Left: View of the subject's arm avatar and arm workspace for the VR training. Right: Therapist's control screen showing patient information and training parameters.

calculations of Kalman gains for elbow and wrist also account for shoulder and elbow error covariance respectively. Segment lengths are updated after each measurement step. Objects to be reached in VR are determined before training based on the subject's arm range of motion. The RANSAC algorithm (Fischler and Bolles 1981) is used to fit the recorded arm positions into the plane to reduce measurement errors.

Subjects and subject recruitment. Participants will be allocated by random numbers to either an *experimental group* that will receive JEA feedback (randomized with catch trials) or a *control group* that will receive no JEA feedback. **Blinding:** The sequence of allocation will be concealed from those assigning participants to groups until the moment of assignment, to prevent them from consciously or unconsciously influencing which participants are assigned to which groups. Participants will also be blinded to group allocation. Finally, evaluators will be blinded by concealing participant group allocation.

Patients will be recruited through well-established procedures at the JRH. Potential participants will be identified from chart or database review and sent a letter of information describing the study. If they are interested, they will be directed to contact the research assistant by phone or email who will schedule them for a screening interview. Healthy subjects will be recruited from the community with the help of information flyers posted on bulletin boards. Subjects will participate after signing informed consent forms approved by the Center for Interdisciplinary Research in Rehabilitation (CRIR) Ethics Committee. Handedness will be measured for both studies with the Edinburgh Handedness Inventory (Oldfield 1971) but for Study 2, both right- and left-handed subjects will be included since hemispheric dominance is not expected to influence results. For Study 1, healthy women and men will be included who 1) are between the ages of 18-75 yrs; 2) have normal or corrected-to-normal vision; and 3) are able to provide informed consent. For Study 2, women and men will be included who 1) sustained a first cortical/sub-cortical ischemic/hemorrhagic stroke <1 yr previously and are medically stable; 2) are aged 18-75 yrs to minimize confounding effects of age-related changes in muscular responses; 3) are no longer receiving treatment; 4) have arm paresis (Chedoke-McMaster Arm Scale of 2-6 /7; Gowland et al. 1993) but are able to perform voluntary elbow movement of at least 30° per direction; 5) have mild-moderate elbow flexor spasticity; and 6) are able to provide informed consent. Subjects will be excluded if they have/are: 1) other major neurological neuromuscular/orthopaedic/pain problems that may interfere with task performance; 2) major cognitive deficits (<26 on Montreal Cognitive Assessment; Nasreddine et al. 2005) or 3) depression (> 14 on Beck Depression Inventory II; Beck et al. 1988; 1996).

[figure not shown]

Fig. 3. UL model based on the Kinect II skeleton (left) and explanation of the extended Kalman filter (right) to improve motion tracking accuracy.

Data analysis

For Study 2, data from Canada will be combined with those from Israel for a total of 12 subjects per group.

To address Hypothesis 1, we will compare the change in the IP between the Pre-Test and the Post-Test as an indicator of motor improvement and the change from Post-Test to Follow-Up as an indicator of motor learning using paired t-tests after verifying for data normality.

To address Hypothesis 2, changes in the area of the active control workspace and clinical scores will be compared between groups using paired t-tests after verifying for data normality.

Knowledge translation

The preliminary results will primarily be used to inform the design of a full randomized controlled trial. However, preliminary results will be shared with clinicians at both sites and by oral or poster presentations at local, national or international meetings.

Participating researchers

[name] is a 1st year Master's student in the Integrated Program of Neuroscience at McGill University. **[name]** is Professor in the School of Physical and Occupational Therapy in the Faculty of Medicine at McGill University. She has pioneered many innovations in the area of upper limb rehabilitation, including identification of underlying motor control deficits at the joint and interjoint level, measurement of spasticity, incorporation of VR training interventions and the distinction between compensation and recovery. **[name]** is an Associate Professor in the Department of Industrial Engineering and Management at Ben-Gurion University of the Negev. She leads the Telerobotics laboratory where robotic motion control, learning, and interaction methodologies are developed and assessed. [name] has applied advanced mathematical methods for modeling and analysis of arm motion in healthy subjects and in patients with stroke. **[name]** is a Senior Lecturer in the Department of Physiotherapy who has been studying human movement in health and in disease for over a decade, publishing in journals that are either specific to neurological rehabilitation, or appropriate for inter-disciplinary research (e.g., in *Scientific Reports*). Profs. [name] and [name] have been collaborating on stroke rehabilitation for close to a decade. They have jointly published papers in leading journals and conferences [e.g., 15-17] and have worked together in two funded research projects. [name] and [name] have collaborated on robotic rehabilitation, and have jointly supervised a student working on robotic mirror-game treatment [18].

Budget and matching funds: details and justification

The project is funded by an ABC (Agricultural, Biological and Cognitive Robotics) grant to [name] from Ben-Gurion University for the portion of the research done in Israel. Funds are allocated for supporting a scholarship or a graduate student. During the first year, most of the funds were allocated to the construction of the passive manipulator and purchase of equipment (i.e., computer, Montreal Spasticity Measure). Funds are allocated for subject compensation, publications and student travel to conferences.

Table 1. ABC budget Israeli team

Funding plan per fiscal year k US\$	Y - 1	Y - 2	Y - 3	Total
Scholarship for graduate student	2	2	2	

Building manipulandum + computer for the system	11		
Spasticity measurement equipment	9.5		
Supplies, peripherals, software license, Kinect, etc.	1	0.5	2
Human subject reimbursement	2		3
Travel: To Canada (year 2) Hosting in IL (year 1+3)	1	1	2
Student travel to conferences			3
Publications			3
Total k US\$	15	15	15
			45

Justification: Most of the budget in the first year is allocated to adapting the current robot/manipulandum and writing/implementing appropriate software for EA. Personnel costs are related to this activity in year 1 and to conducting the study in years 2 and 3. Human subject reimbursement (\$25 x 14 sessions (3 test + 10 training) x 12 subjects = 4200). Funds are allocated to defray travel costs to Israel in year 1 and 3 and hosting costs in Canada in year 2 for PI and students, as well as to defray costs of publication and presentation in years 2 and 3.

Table 2. Matching budget Canadian team

Matching funding is provided by [name] from the Canada Research Chairs fund (until March 2019) and then the Distinguished James McGill Professor fund.

Funding plan per fiscal year k US\$	Y - 1	Y - 2	Y - 3	Total
Personnel (Research assistant + engineer)	10			10
Personnel (Research assistant + student)		10	10	20
Adapting manipulandum, software + computer for the system	3			3
Supplies, peripherals, software license, Kinect, etc.				
Human subject reimbursement	2	2		4
Travel: To IL (year 1+3) Hosting in Canada (year 2)	2	1	2	5
Conference presentation and publications	2	1		3
Total k US\$	15	15	15	45

References

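### Any temporary fatigue at the Post-Test would lower measured improvement and raise measured motor learning equally; no rest is scheduled before that test, and no Pre-Test to Follow-up contrast is planned

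*Combined protocol and SAP*

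**What the plan says.** The session timetable in the protocol's Research plan places the three reaching tests as follows.

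- **Pre-Test:** "Session 1 (1 hour and 15 min) will include a Reaching Pre-Test of 10 trials to a fixed target". It is done before training.
- **Post-Test:** "the last 10 trials of Session 3 will be done to a fixed target (Post-Test". The description of the robotic set-up words it differently: "The same protocol will be added to the end of Session 3 as a Post-Test and repeated 1 hour after Session 3 as the Follow-up".
- **Follow-up:** "there will be a pause of 1 hour after the training and then a Reaching Follow-up Test".

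Under Training Protocol, a session lasts at least 30 minutes, about 138 reaches, and "practice will be extended to the time needed to complete 138 reaches per session". The Research plan allows rest as needed against fatigue in both studies, but ties no rest to the Post-Test. Perceived effort "will be evaluated with the valid and reliable 20 pt Borg Rating of Perceived Exertion Scale" at the end of each training session. The IP analysis does not use that rating.

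For Hypothesis 1, the Data analysis section takes Pre-Test to Post-Test change in IP as improvement and "the change from Post-Test to Follow-Up as an indicator of motor learning", both by paired t-tests. It plans no Pre-Test to Follow-up contrast for IP.

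**The concern.** IP change is a primary outcome in both studies and reflects reaching efficiency. Its three measurements fall at different points relative to exertion: before training, directly at the end of a training session, and an hour later. The Post-Test enters both change scores with opposite sign, so anything that temporarily depresses it moves the two in opposite directions. Recovery from tiredness over the hour could then be read as learning, and real improvement could be understated.

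The plan itself regards fatigue as possible: it offers rest against it, and perceived effort is a secondary outcome in Study 2. The report of no fatigue comes from 21 healthy adults with a mean age of 26.2 years after one 30-minute period. Study 2 enrols people with moderate-to-severe stroke aged 18 to 75. The results are meant to inform a full randomised trial, so an ambiguous learning measure would carry forward.

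**Working it through.** **1. The plan's own figure.** The only relevant figure is about 138 reaches in 30 minutes. The inputs, from Training Protocol, are 3 s per reach and objects presented every 2 to 10 s. At the longest interval, 1800 / (3 + 10) = 138.5, which reproduces 138. At the mid-range interval of 6 s, 138 reaches take 138 × 9 / 60 = 20.7 min, so the 30-minute minimum governs. Practice runs beyond 30 minutes only if the mean reach time exceeds 1800/138 − 6 = 7.0 s at a 6 s interval, or 1800/138 − 10 = 3.04 s at a 10 s interval. Time spent actually reaching is 138 × 3 s = 6.9 min, or 23% of 30 min.

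**2. The Post-Test's place in the count.** If its 10 trials are the last ones within the 138, there are 138 − 10 = 128 training reaches. If they are added, the session has 138 + 10 = 148 reaches. The two descriptions do not agree on this.

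**3. Algebra.** Let L be the true gain by the end of training, R the true change over the following hour, and f any temporary decrement at the Post-Test.

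- Pre-Test to Post-Test = L − f
- Post-Test to Follow-up = R + f
- Pre-Test to Follow-up = L + R, free of f if both tests are taken in a comparable state

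With assumed L = 0.8 SD, R = 0 and f = 0.5 SD, improvement reads 0.3, learning reads 0.5, and Pre-Test to Follow-up reads 0.8.

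**4. Between arms.** The contrast in Post-Test to Follow-up change is (R₁ − R₀) + (f₁ − f₀). With f₁ = f₀ the second term vanishes and the error rate stays at 5%.

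**5. Sensitivity.** The documents give no f, SD or alpha. Assumed: f, or its difference between arms, of 0.2, 0.5 or 0.8 SD of the change score; two-sided alpha 0.05; true Post-Test to Follow-up change zero (within arm) or equal (between arms). Rejection probabilities come from the noncentral t distribution. The within-arm paired test has n = 12, 11 degrees of freedom and noncentrality f√12. The between-arm test has 12 per arm, 22 degrees of freedom and noncentrality (f₁ − f₀)√(12/2).

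| Assumed size (SD) | Within-arm test, fatigue = size | Between-arm test, fatigue difference = size |
|---|---|---|
| 0 | 5% | 5% |
| 0.2 | 9.7% | 7.6% |
| 0.5 | 35.3% | 21.6% |
| 0.8 | 71.4% | 46.6% |

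**6. Which test is planned.** Read literally, a paired t-test for Hypothesis 1 compares two occasions within one arm, where nothing cancels. For Hypothesis 2 the same section applies paired t-tests to a comparison between groups, so the label alone does not settle the question.

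**The case against.** A reader might infer that the Post-Test is taken without rest in tired participants, so that the learning result is biased. The documents do not support that much.

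- **Rest exists.** It is available as needed. What is missing is a scheduled, standard interval before the Post-Test.
- **Fatigue is not shown.** The arm is supported, reaching fills about 23% of a 30-minute session at 3 s per reach, and the preliminary study reported no fatigue. That study does not settle the stroke case, but it weakens any claim of fact covering both studies. Warm-up could also act the other way; f would then be negative, and the algebra holds with the signs reversed.
- **The extension is not universal.** Only slower participants would run past 30 minutes.
- **Randomisation protects the main contrast.** Hypothesis 1 compares joint error augmentation (JEA) with none, on one timetable with a common reach target. Equal fatigue cancels.
- **The other tests are not assured to be rested.** In the stroke group, clinical evaluations precede Session 1 and follow Session 3, and neither is timed against the reaching tests.
- **Effort is already rated** at the end of each session, so it can be compared by arm.

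All of these stand as limits on the point. They do not remove it. As-needed rest can vary by participant and arm. Workloads are not identical either: in the stroke group, workspace extensions are added for JEA patients, and targets progress by active range in the JEA arm but by fixed 2 cm steps in the other. In the preliminary study the error-augmentation group tended to work longer, although that study is not described as fixing the reach count. Unequal fatigue is therefore possible, but not demonstrated.

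**Conclusion.** The point holds in conditional form, as an inexpensive improvement worth making. The Post-Test has no scheduled rest before it and enters both IP change scores with opposite sign, and no planned IP contrast avoids it. Any temporary decrement there shifts improvement and learning one-for-one in opposite directions. That is algebra and needs no assumed size.

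Whether it affects the conclusions depends on two things the documents leave open: whether the paired t-tests are run within arm, and whether fatigue differs by arm. With the assumed 0.2, 0.5 or 0.8 SD, false-positive rates for learning would be about 10%, 35% or 71% within arm. They would be about 8%, 22% or 47% between arms if fatigue differed by those amounts. These figures show sensitivity only; they are not evidence that fatigue of that size will occur. The documents do not support saying that the JEA versus no-JEA comparison is biased.

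**What to change.** 1. Run the Post-Test as a separate 10-trial block after a short standard interval, identical in both arms. Take a Borg rating just before the Post-Test and again just before the Follow-up, and report both by arm.
2. State the interval before each reaching test, including its timing relative to the stroke group's clinical evaluations before Session 1 and after Session 3.
3. Reconcile the two descriptions of the Post-Test: last 10 trials of Session 3, or added to its end.
4. In Data analysis, add a between-arm Pre-Test to Follow-up comparison, for example Follow-up IP adjusted for Pre-Test IP, as the retention measure. State whether each planned t-test is within or between arms.

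Item 4 uses data already collected and does not involve the Post-Test. The rest costs protocol wording, a few minutes in one session and two single-question ratings. The downside is that the Post-Test becomes slightly less immediate, so a very short-lived effect may fade before it is measured.

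### Does the stated pacing fail to give about 138 reaches in 30 minutes, and so leave the amount of practice uncontrolled?

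*Combined protocol and SAP*

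**What the plan says.** The Training Protocol paragraph, which applies to both studies, gives the pacing as "Objects to be reached are randomly presented within the virtual workspace every 2-10s". It describes training as "a session of at least 30 minutes (approximately 138 reaches, considering 3s/reach") and adds: "To control training intensity, practice will be extended to the time needed to complete 138 reaches per session".

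The training time also appears in two other places. The Research plan says "Subjects will perform ~30 min of target reaching with their non-dominant/affected arm, 3 times in one week", and the training section with Fig. 1 says "Three 30 min training sessions will be done".

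Three further statements affect how long one reach cycle lasts:

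- Each reach starts from a specified position (Training Protocol).
- "Feedback in the form of task success of endpoint (hand) movement is presented at the end of each reaching trial" (Training Protocol, continued).
- "Rest periods will be provided when needed to avoid subject fatigue" (Research plan).

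The plan gives no duration for return to start, feedback or rest. It does not say whether rest counts towards the 30 min, how the 2 to 10 s times are distributed, or whether they are a gap after a reach or the time from one presentation to the next.

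**The concern.** The only timing offered beside the figure of 138 is 3 s per reach. Taken alone, that gives 1800/3 = 600 reaches in 30 min, and adding a mid-range gap still gives well over 138. So the number looks wrong.

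The plan presents the 138-reach clause as its control of training intensity. If most participants pass 138 well before 30 min, the clause never operates, the time minimum decides, and the number of reaches varies with pace. In a motor-learning study the amount of practice matters. The results are meant to inform a full trial, so 138 per session could be carried forward when more were in fact delivered. Study 2 also combines two sites, which might read the end of a session differently.

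**Working it through.** **Inputs.** From the Training Protocol paragraph: session minimum 30 min = 1800 s; reach time 3 s; presentation time 2 to 10 s; stated count about 138. Assumption: a mean presentation time of 6 s, the midpoint of the range, since the plan gives no distribution.

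**1. Reproduce the plan's figure.** Reaches = 1800 / cycle time. With the longest gap added to the reach, the cycle is 10 + 3 = 13 s and 1800/13 = 138.46, which rounds to 138. Conversely, 138 × 13 = 1794 s = 29.9 min. Working back from exactly 138 gives 1800/138 = 13.04 s per cycle, or 10.04 s beyond the reach. The 0.04 s above the 10 s maximum is rounding, under a figure labelled approximate.

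**2. Other paces.**

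| Reading of 2 to 10 s | Cycle | Reaches in 30 min | Time for 138 |
|---|---|---|---|
| Gap of 10 s + 3 s reach | 13 s | 138.46 | 29.9 min |
| Gap of 6 s + 3 s reach | 9 s | 200 | 20.7 min |
| Gap of 2 s + 3 s reach | 5 s | 360 | 11.5 min |
| Onset to onset, 10 s | 10 s | 180 | 23.0 min |
| Onset to onset, 6 s | 6 s | 300 | 13.8 min |

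Of these, only the gap reading at its 10 s maximum gives 138. The onset-to-onset reading cannot give it, because its lowest count is 180. The gap reading is therefore the better account of how the figure arose, and under it 138 is the count at the slowest stated pace. In a simulation of 20,000 sessions with gaps uniform on 2 to 10 s and no other time, the mean was about 200 reaches in 30 min (95% range 192 to 207), and 138 were always completed before 30 min.

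**3. Time the plan does not quantify.** Let r be the extra seconds per reach for return, feedback and rest, with a 6 s mean gap, so the cycle is 9 + r.

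| r | Reaches in 30 min | Time for 138 |
|---|---|---|
| 0 s | 1800/9 = 200 | 20.7 min |
| 2 s | 1800/11 = 164 | 25.3 min |
| 4 s | 1800/13 = 138 | 29.9 min |
| 6 s | 1800/15 = 120 | 34.5 min |

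The break-even value is 13.04 − 9 = 4.04 s per reach. Over a session that is 1800 − 138 × 9 = 558 s = 9.3 min. Above it, the extension to 138 operates.

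**4. What ends a session.** The time clause sets a minimum, and the reach clause only lengthens practice. Read together, a session ends when both 30 min and 138 reaches have been reached. Nothing in the text permits stopping at 138 before 30 min. The two clauses are compatible as a joint minimum.

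**The case for a change.** The strongest case for a change is that the reader is told to expect about 138 reaches on the strength of 3 s per reach, when the figure holds only if every gap is at its maximum. Randomly varied gaps would not average 10 s. With a 6 s mean gap and no other time, 138 is 69% of the 200 reaches delivered (138/200), and the clause offered as the control of intensity does nothing. Allowable movement time is also shortened as participants progress, which moves later sessions further from the slowest pace. A pilot that feeds a full trial should state its practice amount correctly.

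Part of this stands. The derivation is not disclosed, the wording reads as an expected count when the number fits the slowest pace, and a minimum does not fix the count for faster participants.

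The rest is weaker. The figure of 200 rests on an assumed mean gap and on no time at all for return to start, feedback or rest, although the plan provides for each of them. For participants slower than 13.04 s per cycle, rest included, the clause does operate, which is plausible in the stroke group. The plan does not promise equal counts, so a guaranteed minimum is a reasonable meaning of controlling intensity. The text shows no difference between arms or sites. If one arose, it would bear on whether an effect is due to the feedback itself or to the amount of practice, and would leave the validity of the randomised comparison intact. Carrying 138 into the next trial by mistake is possible but speculative, since that trial's designers would be expected to look at what was delivered.

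**Conclusion.** The arithmetic claim does not hold: 138 follows from the stated 10 s maximum gap, 3 s reach and 30 min, to within rounding. What is left is missing detail about where the figure came from and the fact that 138 is a minimum. Assuming a 6 s mean gap, the excess over 138 in 30 min ranges from 62 reaches (200 − 138) with no other time per cycle to nil at about 4 s per reach. The documents do not allow a choice within that range.

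Anyone running a session from the text would deliver at least 30 min and at least 138 reaches, under the same rule in both arms. Noting how 138 was obtained, or tabulating delivered reaches and minutes, would be ordinary reporting. It would alter neither the design, the sample size, the analysis nor the conclusions. This is a gap that investigators and analysts can fill sensibly, and no change to the plan is needed.
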